The effect of 4.5 gram methylprednisolone administered as weekly infusions for 12 weeks on bone metabolism in Graves' orbitopathy

Background

Systemic glucocorticoid (GC) (peroral or intravenous) is used in the treatment of numerous diseases.

Treatment with GC is often long-term and many patients therefore develop side effects [1]. One such is decreased bone mineral density (BMD) [2] and increased risk of fractures [3]. There is solid evidence that a daily intake of GC equivalent to 5 mg prednisolone both decreases BMD and increases fracture risk [4], and epidemiological studies show that a yearly cumulative dose of 450 mg prednisolone is harmful [5].

Moreover, GC affect bone structure [6] which increases fracture risk independently of BMD [7]. A diagnosis of osteoporosis is usually given by a BMD T-score ≤ -2.5 but in case of GC treatment anti-osteoporotic treatment may be initiated already at a T-score < -1 . It is common practice in Denmark to commence supplementation with calcium and vitamin D and measure BMD at planned treatment with GC of more than 450 mg prednisolone per year.

There are also studies, however, showing that the effect on bone with GC treatment for up to 20 weeks is largely reversible [8]. At present there is no evidence that short term high-dose GC treatment affects bone mass or increases fracture risk. An epidemiological study shows that daily rather than cumulated dose relates to fracture risk [9] and a recent Danish study shows that prednisolone at a cumulative dose of 1425mg given as 175mg once every 3. week followed by 100mg daily for three days every 3. Week as an adjunct to chemotherapy in treatment of breast cancer does not affect BMD [10].

Graves Orbitopathy (GO) is an eye disease seen with autoimmune hyperthyreosis (Grave's disease). If treatment is warranted intra-venous methylprednisolone with a weekly infusion for 12 weeks is used. Total dose amounts to 4500mg. The present study evaluates the effect of that treatment regimen on bone.

Purpose

To evaluate if high-dose intra-venous GC in GO affects BMD, bone turnover, or bone structure.

Studypopulation and methods

30 adult (age ≥ 18 år) patients with GO in whom GC treatment is indicated.

Primary end point:

- Change in lumbar spine BMD measured by Dual X-ray Absorptiometry (DXA)

Secondary end points:

- Change in BMD at the hip measured by DXA
- Change in bone turnover measured by CTx and P1NP
- Change in bone structure measured by High Resolution peripheral Quantitative Computed Tomography (HRpQCT)

Inclusioncriterion:

- Patients with GO commencing treatment with GC.

Exclusionscriteria:

- Treatment for osteoporosis
- Primary hyperparathyroidism
- Hypoparathyroidisme
- D-vitamin < 20mmol/L
- Chronic kidney disease with eGFR < 30 mL/min
- Liverdisease
- Peroral treatment with GC three months prior to study

Treatment of Graves' orbitopathy

Patients are treated with intravenous methylprednisolone 500 mg once weekly for 6 weeks followed by 250 mg once weekly according to Danish national guidelines. Dose can be changed according to the clinical response at the discretion of the treating physician but if so the patient is excluded from the study. In addition al patients will be advised to take supplementation with 800 mg calcium and 40 µg 25-OH-vitamin D in 2 daily doses.

Treatment of thyrotoxicosis

Patients will be treated according to national guidelines.

Examinations

Bone Mineral Density is measured using DXA at the hip and spine regions at baseline and again after 12 and 24 weeks. Baseline DXA may be performed until 10 days after first dose of GC. Bone turnover is measured in blood samples using the bone markers P1NP and CTx. Blood samples are taken at baseline and after 3, 9, 12, and 24 weeks.

Bone structure is evaluated using high resolution peripheral quantitative computed tomography (HR-pQCT) at baseline and after 12 weeks.

In addition the following is measured at baseline to investigate for exclusion criteria:

- Creatinine
- Na^+
- K^+
- Parathyroid hormone
- Calcium
- Vitamin D
- Alanine aminotransferase
- Alaline phosphatase
- Bilirubine

Studyplan:

Statistics

Power calculation is based on the primary end point. From previous studies we know that the standard deviation on change in BMD is 3%. With a significance level of 5% and a power of 90% we need 30 participants to demonstrate a change in BMD of 2% using a paired samples t-test. A change below 2% is considered clinically insignificant. Change over time based on 2 measurements will be evaluated using paired samples t-test and change over time with more than two measurements will be calculated with ANOVA with repeated measures.

Recruitment

Participants will be recruited from Department of Endocrinology and Internam medicine, Aarhus University Hospital, Denmark during visits in the outpatient clinic. Here, written and oral information is given to the

potential participants in a closed room by one of the study doctors. Potential participants are encouraged to read the information thoroughly and are informed that they have the right to a bystander and are given a week to considerate participation before signing any informed consent form.

Biobanks

During the study a research biobank is formed to store blood samples (4 tubes with 2mL of both serum and plasma. To minimize analytical variance bone markers are analysed in batches when the last participant is finished. Thus, the research biobank is terminated in march 2021 and excess material is transferred to a biobank at Aarhus University Hospital for future research. Here, material is stored for future research for a maximum of 10 years before destruction. Participants are informed that at any time they can request their material to be destroyed.

Perspectives

Many patients are treated wit GC for a variety of disease with both intermitent or continuous dosing. It is therefore important to disclose which patients should receive a DXA and start medical fracture prevention, so that future treatment can be given with the greatest precision.

Etiske overvejelser

Blood sampling can give a bruise and in rare cases a skin infection. HR-pQCT and DXA gives a radiation dose of $80\mu\text{Sv}$ and $12\mu\text{Sv}$, respectively, which increases the life-time risk of cancer by 0,0005% from 25,0% to 25,0005%.

All participants are otherwise treated for their diseases according to national guidelines. We therefore believe that the benefit from the knowledge gained in the study outweighs the risks.

The project is approved by the Danish Data Protection Agency and Regional Ethics Comitee.

Economy

The study is initiated by the sponsor who already has acces to DXA and HR-pQCT and staff to use these. The costs for blood samples will be covered by the sponsors research account and does not call for additional funding. Participants will receive no participation fee.

Publications

All results (positive and negative) will be attempted to be published in a peer reviewed scientific journal. Participants will be given written information about the results and can get additional information by addressing the sponsor.

References

1. Bond WS (1977) Toxic reactions and side effects of glucocorticoids in man. *Am J Hosp Pharm* 34:479–85.

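### The prior-glucocorticoid exclusion names only the peroral route, so a patient with recent intravenous glucocorticoid may be eligible with a possibly affected baseline

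*Combined protocol and SAP*

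**What the plan says.** The opening sentence of the Background puts both routes under one heading: "Systemic glucocorticoid (GC) (peroral or intravenous) is used in the treatment of numerous diseases". The regimen under study is intravenous: "Patients are treated with intravenous methylprednisolone 500 mg once weekly for 6 weeks followed by 250 mg once weekly", which over 12 weeks comes to 4,500 mg.

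Eligibility is set by one inclusion criterion, "Patients with GO commencing treatment with GC", and a short list of exclusions. The only exclusion about earlier GC is "Peroral treatment with GC three months prior to study". The others concern osteoporosis treatment, parathyroid disease, vitamin D, kidney function and liver disease.

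The Examinations section lists laboratory tests at baseline to check the exclusions. It asks for no record of earlier GC exposure. The primary endpoint is the change in lumbar spine BMD on DXA, and there is no control group. The Statistics section does not adjust for earlier GC.

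**The concern.** A washout for earlier GC protects the baseline. The plan has one, so the sponsor has already judged that recent GC makes a patient unsuitable. It covers one of the two systemic routes that the protocol names, and leaves out the route of the study drug.

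At stake is the meaning of change from baseline. The Background cites studies "showing that the effect on bone with GC treatment for up to 20 weeks is largely reversible". If that carries over to intravenous pulses, a recently treated patient may be regaining bone when measured at baseline, and the recovery would offset loss from the new course. If instead loss from the earlier course is still going on, it would add to the measured loss. In either case the patient's 12- and 24-week values reflect more than the 4.5 g in the title. With no comparison group, nothing in the design cancels this. The CTx and P1NP baselines are open to the same problem.

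**Working it through.** **1. Does the text leave the gap?** Take the criteria in turn.

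- The exclusion names the peroral route only. Since the Background distinguishes peroral from intravenous, the word cannot be read as meaning any systemic GC.
- The inclusion criterion requires that the patient is starting GC. It does not require a first course or no earlier GC. If it already ruled out recent GC, the separate peroral exclusion would be redundant.
- No other exclusion, and none of the listed baseline tests, would identify earlier intravenous GC.

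This leaves two kinds of patient who may be eligible: one who finished an intravenous course within the three months and starts another, and one who had intravenous GC for another disease in that time.

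**2. The plan's own sample size.** Inputs from the Statistics section: SD of change 3%, change to detect 2%, significance level 5%, power 90%, paired t-test, 30 participants. The number of sides is not stated; I assume two.

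- Normal approximation: n = (3 × (1.960 + 1.282) / 2)² = 23.6, so 24.
- Noncentral t: n = 26 (power 90.4% at 26, 89.2% at 25).
- At n = 30 the noncentrality is (2/3) × √30 = 3.65 and power is 94.2%.

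The stated 30 is therefore more than these inputs require. That discrepancy is on the safe side and separate from this point. I use 94.2% as the base.

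**3. How much could such patients matter?** Let p be their share and d the carry-over offset in percentage points, meaning how much less they lose than the others. The documents give neither; both are assumptions.

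- Mean loss = 2 − p × d
- SD = √(9 + p(1 − p)d²)
- Power from the noncentral t with n = 30, noncentrality = mean / SD × √30

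Worked case, p = 0.10 and d = 2: mean = 2 − 0.2 = 1.8; SD = √(9 + 0.09 × 4) = 3.059; noncentrality = 1.8 / 3.059 × 5.477 = 3.22; power 87.6%.

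| Share | Offset (points) | Mean loss (%) | SD (%) | Power |
|---|---|---|---|---|
| none | – | 2.00 | 3.000 | 94.2% |
| 1 in 30 | 1 | 1.97 | 3.005 | 93% |
| 1 in 30 | 2 | 1.93 | 3.021 | 92% |
| 1 in 30 | 3 | 1.90 | 3.048 | 91% |
| 10% | 1 | 1.90 | 3.015 | 91.5% |
| 10% | 2 | 1.80 | 3.059 | 87.6% |
| 10% | 3 | 1.70 | 3.132 | 81.9% |
| 20% | 1 | 1.80 | 3.027 | 88.3% |
| 20% | 2 | 1.60 | 3.105 | 77.9% |
| 20% | 3 | 1.40 | 3.231 | 63.1% |

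An offset of 1 means that these patients lose half as much as the others. An offset of 2 means they lose nothing. An offset of 3 means they gain 1% while receiving the full course.

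**4. Direction.** The table assumes recovery, so d is positive. If earlier loss is continuing, d is negative and the mean loss is overstated: with p = 0.10 and d = −1 it is 2 + 0.1 = 2.1%. A stable earlier loss largely cancels in change from baseline.

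**The case against.** The strongest objection is that the gap may have no practical effect. The documents describe a single 12-week course. They do not mention relapse or repeat courses, and they give no frequency for either. That intravenous methylprednisolone is the treatment used for GO does not show that candidates have already had it. This stands: the share may be zero, and then so is the effect.

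Second, a reader might infer that any such patient enters with a baseline already lowered by GC. The documents do not support that. The Background says that evidence is lacking for an effect of short-term high-dose GC on bone mass, which is the question the study asks. It also cites an intermittent 1,425 mg prednisolone regimen that did not affect BMD. By its title, the study cited for reversibility concerns low-dose prednisone in rheumatoid arthritis, so carrying it over to intravenous pulses is an assumption. An affected baseline is a possibility only.

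Third, a reader might infer that the bias must run towards no effect. That holds if the patient is recovering. Continuing loss would pull the other way.

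Fourth, it is tempting to say that a patient already part-way through the current course could enter. That patient is arguably not commencing GC, and the timing rule "Baseline DXA may be performed until 10 days after first dose of GC" ties baseline to the start of a course. The gap is limited to the two kinds of patient identified above.

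Finally, the largest losses of power need an extreme case. The 63% figure takes six of 30 patients, each gaining bone during treatment.

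These objections limit the size and certainty of the harm. They do not close the gap in the wording.

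**Conclusion.** The concern holds as a gap in the eligibility wording, and closing it is a cheap improvement. As written, recent intravenous GC from a completed course or for another disease does not exclude a patient, while recent peroral GC does, and the plan gives no reason for treating the routes differently.

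The consequence is a possible bias in within-patient change, of uncertain direction and unknown frequency. Under the assumed offsets, one such patient in 30 costs at most about 3 points of power (94.2% to 91%) and leaves it above the planned 90%. Three patients bring it to between 91.5% and 81.9%, and six to between 88.3% and 63.1%. These figures assume a true loss of 2%, SD 3%, a two-sided test, all 30 patients analysed, and carry-over of 1 to 3 points towards no loss. They show what could happen; they do not predict what will.

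A reader might go further and, because the Background states that "epidemiological studies show that a yearly cumulative dose of 450 mg prednisolone is harmful", ask for a cumulative-dose limit as well. That is a separate design preference, and this point does not rest on it. The same Background also cites a study relating fracture risk to daily rather than cumulated dose.

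**What to change.** Reword the exclusion so that it covers systemic GC, peroral or intravenous, in the three months before the study. The window stays as it is and the sample size does not change.

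If any such patients are already enrolled, record the route, dose and stop date of their earlier GC, and repeat the primary analysis without them as a sensitivity analysis.

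The cost is one amended line, checked against the medication history, with no new procedure. The downside is that a few re-treated patients become ineligible, so recruitment may be slightly slower.
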